##### **5.4.5.2. Safety – Extension Study Period Subset**

The safety population – Extension Study Period subset will consist of all patients in the safety population who have received at least one (full or partial) dose of study drug during the Extension Study Period.

The safety population – Extension Study Period subset will be the primary population subset for the summary of Extension Study Period safety data.

#### **5.5. Definition of Baseline**

The baseline value will be considered to be the last non-missing value before the first infusion. Post-baseline visits will be considered to be all visits after the first date of infusion.

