- 9. All scheduled 12-lead electrocardiograms (ECG) must be performed after the patient has rested quietly for at least 5 minutes in the supine position. On the day of infusion, 12-lead ECGs will be also performed after 1 hour (±15 minutes) after the end of the study drug infusion for the hypersensitivity monitoring. At Extension Week 0, 12-lead ECG will be performed prior to study drug infusion. If Extension Week 0 is conducted on the same day with Week 48, assessment result of 12-lead ECG performed prior to study drug infusion will be used for the ECG assessment to be performed at Week 48.
- 10. Additional vital signs including blood pressure, heart and respiratory rates, and body temperature (before administration [within 15 minutes prior to the beginning of the study drug infusion], within 15 minutes after the end of the study drug infusion, and at 1 hour [±15 minutes] after the end of the study drug infusion) will be assessed to monitor for possible hypersensitivity reactions. In addition, hypersensitivity should be monitored by routine continuous clinical monitoring including ECG (12-lead) monitoring 1 hour (±15 minutes) after the end of the study drug infusion. Emergency equipment and medication, such as adrenaline, antihistamines, corticosteroids, and respiratory support including inhalational therapy, oxygen, and artificial ventilator must be available.
- 11. ACR20, ACR50, ACR70, and hybrid ACR will be calculated from these assessments. It is recommended that the joint count assessments are performed by the same physician when possible.
- 12. Twenty eight tender and swollen joints, ESR or CRP, and patient's general health or global disease activity measured on VAS will be assessed for DAS28 calculation. The European League Against Rheumatism response criteria will be derived from the DAS28.
- 13. Patients with B-cell, IgM and IgG values below the LLN or less than 50% of their baseline value of Main Study Period should be monitored every 8 weeks (±14 days) after the study completion until recovery is achieved for one of them (equal to or higher than the lower limit of normal OR at least 50% of the baseline value of Main Study Period). Upon the study completion, additional follow-up of B-cell, IgM and IgG monitoring will be determined by the Data Safety Monitoring Board (DSMB).

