**Figure 3: Study Schematic of Randomization**

Patients, who are assigned to receive CT-P10 with their first infusion in the study, will be considered as group 1 and maintain CT-P10 for the third course.

Patients, who are assigned to receive Rituxan with their first infusion in the study, will be randomized in a 1:1 ratio to group 2 (CT-P10 will be administered for the third course) and group 3 (Rituxan will be maintained for the third course) at Extension Week 0.

Patients, who are assigned to receive MabThera with their first infusion in the study, will be considered as group 4 and receive CT-P10 for the third course at Extension Week 0.

The third course of treatment will be initiated between Week 48 and Week 52 of the Entire Study Period if patients become eligible according to the predefined safety criteria for the course based on the results assessed within 8 weeks from the Extension Week 0. A visit window is not permitted on the day of second infusion for the third course of treatment.

Unscheduled visit(s) can be conducted for assessment of safety criteria until the initiation of the third course of treatment.

For patients who receive the third course of treatment at Week 48, the scheduled assessments and samplings should be performed according to the schedule of events and sampling schemes for the Extension Week 0. Otherwise, all scheduled assessments for Week 48 should be performed separately from the Extension Week 0 according to the schedule of events for Main Study Period.

All patients will receive MTX and folic acid concomitantly. Each patient may receive up to 3 courses of treatment; the first course will be an infusion of study drug (CT-P10, Rituxan, or MabThera) at Week 0 and Week 2. If patients meet the predefined safety criteria, patients are eligible to receive the additional course(s) of study drug (2 infusions in each course with a 2-week interval between infusions) at the discretion of the investigator.

For the second course of treatment in the Main Study Period, patients, who do not meet the predefined safety criteria, will not receive an additional course of treatment, but they will be followed according to the schedule of events for Main Study Period.

For the third course of treatment in the Extension Study Period, patients, who do not meet the predefined safety criteria within the time frame for the study drug infusion, will not receive an additional course of treatment and will be terminated from the study.

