### **5.7. Display of Data by Treatment**

All analysis result of Main Study Period excluding ANCOVA will be displayed by the following groups: CT-P10, Rituxan, MabThera, and combined Rituxan and MabThera group.

Analysis of the general and PK section in Main Study Period will be conducted in Part 1 and 2 separately.

All analysis result of Extension Study Period will be displayed by the following groups: CT-P10 maintenance (Group 1), Switched from Rituxan (Group 2), Rituxan maintenance (Group 3), Switched from MabThera (Group 4), and combined Switched from Rituxan and Switched from MabThera group.

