## 6. Patient Disposition

The number of patients who were screened will be displayed. The number and percentage of patients who randomized, initiated, completed, or discontinuing treatment will be displayed using the following categories for all-randomized population and all-randomized population – Extension Study Period subset by treatment group and part.

- Screened
  - Screening Failure
- Randomized
- Initiated first course of treatment in Main Study Period
  - Complete first Course in Main Study Period
  - Discontinued during first Course in Main Study Period
- Initiated second course of treatment in Main Study Period
  - Complete second Course in Main Study Period
  - Discontinued during second Course in Main Study Period
- Initiated treatment in Extension Study Period
  - Complete Extension Study Period
  - Discontinued Extension Study Period

The reasons for screening failure will be displayed using the following categories and ordering:

- Inclusion/Exclusion Criteria Not Met
- Patient Withdrew Consent
- Others

The screening failure summary will include the number of patients out of all screened patients and the primary reason for screening failure. A listing of patients reported as screening failures will also be provided.

The reasons for discontinuation will be displayed using the following categories and ordering:

- Patient develops sign of disease progression
- Patient experiences no efficacy from study drug
- Patient withdraws consent or patient refuses
- Patient develops any malignancy
- Adverse Event
- Significant or major protocol violation
- Lost to follow-up

- Patient died
- Investigator decision
- Sponsor terminates the study
- Pregnancy
- Other

In addition, the treatment duration in days (calculated as date of last visit - date of first infusion in study period + 1) will be calculated and be summarized for patients who discontinue study treatment prematurely. The date of first infusion will be taken as the earliest date recorded on the “Study Treatment Infusion” eCRF page and the date of last visit will be taken as recorded on the “Study Termination” eCRF page.

The disposition listing will list all data collected on the “Study Termination” eCRF along with the date of first infusion for the all-randomized population.

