### 9.1. Prior and Concomitant Medications

Medications will be classed as either prior or concomitant. For the purpose of inclusion in prior and/or concomitant medication tables, incomplete medication start and stop dates will be imputed as follows:

- Missing day: Assume the day is 1st of the month.  
However, if the partial date and the date of first infusion (defined as the earliest date recorded on the “Study Treatment Infusion” eCRF page) lie within the same month and year and the date of first infusion is not after the stop date of the medication, set to the date of first infusion. Otherwise, if date of first infusion is after the stop date for the medication, set to stop date of the medication.
- Missing day and month: Assume January 1st.  
However, if the partial date and the date of first infusion lie within the same year and the date of first infusion is not after the stop date of the medication, set to the date of first infusion. Otherwise, if date of first infusion is after the stop date for the medication, set to stop date of the medication.
- Missing day, month and year: Assume date of first infusion, if not after the stop date for the medication. Otherwise set to the stop date for the medication.

For the missing day imputation, the following examples should be used for reference:

- Example 1:  
Medication start: JUN2016  
Medication end: 20OCT2016  
Date of first infusion: 16OCT2016  
Medication start imputed: 01JUN2016
- Example 2:  
Medication start: OCT2016  
Medication end: 20OCT2016  
Date of first infusion: 16OCT2016  
Medication start imputed: 16OCT2016

- Example 3:  
Medication start: OCT2016  
Medication end: 20OCT2016  
Date of first infusion: 24OCT2016  
Medication start imputed: 20OCT2016

Partial end dates will be imputed as follows:

- Missing day: Assume the last day of the month.
- Missing day and month: Assume December 31st.
- Missing day, month and year: Assume that the medication is continuing.

In the case of the death of a patient, and the imputed end date is after the date of death, the end date will be imputed as the date of death.

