### **13.3. Vital Signs**

Vital signs (including systolic and diastolic blood pressure (BP), heart rate, respiratory rate, temperature, and weight) will be summarized by treatment group for the safety population and safety – Extension Study Period subset at each scheduled collection time. Change from baseline will also be summarized for all post-first infusion scheduled collection times. Baseline will be the last available measurement prior to the first infusion. All vital sign data will be listed for safety population.

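### Extension change and shift tables are measured from before the first-ever infusion, so they mix earlier courses with the third, and no estimate is planned for the re-randomised Group 2 versus Group 3 comparison

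*SAP*

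**What the plan says.** **Baseline.** SAP 5.5 reads: "The baseline value will be considered to be the last non-missing value before the first infusion". It goes on: "Post-baseline visits will be considered to be all visits after the first date of infusion". On that wording Extension Week 0 is a post-baseline visit. SAP 5.5 does not say which first infusion it means, but other sections point to the first in the trial. SAP 6 states: "The date of first infusion will be taken as the earliest date recorded on the" study-treatment infusion eCRF page. SAP 9.1 uses the same definition for medication dates. SAP 13.3 restates the rule for vital signs: "Baseline will be the last available measurement prior to the first infusion". Protocol Table 6, for B-cell and immunoglobulin follow-up after the Extension, names the period outright: "less than 50% of their baseline value of Main Study Period should be monitored".

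**Where it is used.** Change from baseline or shift tables are planned for the Extension subsets in SAP 11.2 (DAS28), 12.1 (PD), 13.2 (laboratory, immunoglobulins, urinalysis), 13.3 (vital signs), 13.4 and 13.5.2 (ECG) and 13.6 (physical examination).

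**Groups.** Rituxan patients "will be randomized in a 1:1 ratio to group 2 (CT-P10 will be administered for the third course) and group 3", who stay on Rituxan. The strata are the number of Main Study courses and EULAR-CRP response at Week 40. SAP 5.7 displays Groups 1 to 4 separately, "and combined Switched from Rituxan and Switched from MabThera group".

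**Comparisons.** The ANCOVAs for PK (SAP 10.3), DAS28 (11.2) and PD (12.2) and the log-rank test for ACR20 (11.1.2) all concern the Main Study Period.

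**The concern.** A column headed change from baseline in an Extension safety table will be read as what happened during the third course. Here it also contains whatever the earlier courses did. Under SAP 4.1 the third course normally starts at Week 48-52 and may start as late as Week 72, after up to two courses. A fall in IgG, or an ECG that became abnormal, during the first year would count as change in the Extension table.

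The second issue is separate. The re-randomisation of Rituxan patients is the only randomised evidence in the trial on moving from a reference product to CT-P10. It is stratified, and Protocol 3.1 takes care to keep it blinded. SAP 2 says that statistical assessments will be direct comparisons between groups. Yet the plan never estimates the one comparison that this randomisation creates, and the Extension strata enter no analysis. The column that is added puts randomised Group 2 together with Group 4, all of whose members switch by design.

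**Working it through.** **1. Figures in the plan.** The documents give no sample size, margin or error rate for the Extension. The only figure borrowed here is the SD of DAS28 change, 1.32 (SAP 5.2). The Part 2 power that uses it reproduces: SE = 1.32 × sqrt(1/133 + 1/189) = 0.149; power = 2Φ(0.50/0.149 − 1.645) − 1 = 91.1%, against a stated 90% or so.

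**2. Does the early baseline bias Group 2 versus Group 3?** It should not: the baseline was measured before the second randomisation, so its expected value is the same in both groups. A simulation agrees. It assumed 67 per group (90% of 149, halved), SD 1.2 at each visit, means 6.0 at Week 0 and 3.5 at Extension Week 0 and Extension Week 24, a switch effect of 0.30 added to Group 2, and 4,000 runs. All these values are assumptions. The SDs below also follow from 1.2 × sqrt(2(1 − ρ)) × sqrt(2/67), where ρ is the correlation of the final value with the baseline used.

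| ρ with Week 0 / with Ext Week 0 | Mean difference, Week 0 baseline | Mean difference, Ext Week 0 baseline | SD of estimate, Week 0 | SD of estimate, Ext Week 0 |
|---|---|---|---|---|
| 0.3 / 0.6 | 0.300 | 0.295 | 0.245 | 0.187 |
| 0.3 / 0.7 | 0.301 | 0.302 | 0.249 | 0.163 |
| 0.5 / 0.5 | 0.297 | 0.298 | 0.206 | 0.206 |

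There is no bias with either baseline. Precision is lost only if Extension visits correlate more strongly with each other than with Week 0.

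**3. Does it affect the within-group figure?** Yes. In the same set-up Group 2 shows 3.8 − 6.0 = −2.2 from Week 0 but 3.8 − 3.5 = +0.3 from Extension Week 0. The first figure is an earlier benefit of 2.5 less a third-course change of 0.3 in the opposite direction.

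**4. Can a reader undo this from the tables?** Only in part.
- *Continuous measures.* With the same patients at both visits, the mean change from Extension Week 0 is the difference of two tabulated means. Its SD is not available, because it depends on a correlation that is not tabulated.
- *Shift tables.* The plan gives Week 0 by Extension Week 0 and Week 0 by Extension Week 24. The cross-table of Extension Week 0 by Extension Week 24 does not follow from these two. Equal numbers abnormal at both visits may be the same patients or different ones.

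**5. How precise would Group 2 minus Group 3 be?** If 50-100% of 149 enter, the groups have 37 to 74 each. The 95% half-width for a proportion is 1.96 × sqrt(2p(1 − p)/n); for DAS28 it is 1.96 × 1.32 × sqrt(2/n).

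| n per group | ADA, p = 10% | ADA, p = 20% | DAS28 |
|---|---|---|---|
| 74 | ±9.7 points | ±12.9 points | ±0.43 |
| 37 | ±13.7 points | ±18.2 points | ±0.60 |

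With the Part 2 margin of ±0.50 and a 90% CI, equivalence power would be 49% at 74 per group and essentially zero at 37. These figures describe the proposed addition, not harm done by the plan.

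**The case against.** The tempting stronger reading is that the Extension cannot isolate the effect of switching. The documents do not support it. Groups 2 and 3 are randomised at Extension Week 0, a common earlier baseline leaves their difference unbiased, and SAP 5.7 shows the two groups separately. The pooled column is an addition and replaces nothing. A reader can work out a crude difference from the counts or means.

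A reader might also infer that earlier falls in IgG or lymphocytes would be hidden. They would not. Both are sampled before dosing at Extension Week 0, actual values are summarised by visit, and SAP 13.2 tabulates immunoglobulins below the lower limit of normal and absolute CTCAE grades by visit. RF and anti-CCP shift tables include Extension Week 0, and patient listings carry the raw values.

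A Week 0 baseline also suits the endpoints. Protocol 7.2.2 asks for DAS28 change, ACR and EULAR response at Extension Week 24 on the same footing as Weeks 24 and 48. Finally, the Extension's stated purpose is additional safety and immunogenicity. No objective or sample-size statement concerns switching, and ADA positivity and infusion reactions are not change scores, so the baseline rule does not touch them.

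All of this stands. What remains is that the within-patient shift and the SD of change over the third course are not in any planned table, and that no stratum-adjusted difference or interval is specified.

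**Conclusion.** The point holds as two modest gaps. First, SAP 5.5 leaves Extension within-group change and shift tables carrying up to two earlier courses, and the planned tables cannot fully undo that. This rests on reading its first infusion as the first in the trial, which SAP 6, SAP 9.1 and Protocol Table 6 support but SAP 5.5 does not say. Second, the randomised Group 2 versus Group 3 comparison is displayed but never estimated.

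Neither gap makes the switching comparison invalid, and neither bears on the Week 24 PK or DAS28 conclusions. The gain from closing them is clearer safety tables and an honest interval on data already collected. That interval would be wide: about 10-14 points for ADA positivity of 10% and 13-18 points for 20%, with entry of 50-100% assumed because the documents give no entry rate.

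**What to change.** - **SAP 5.5.** State that the existing baseline is the last value before the first infusion of the Main Study Period, and keep it for the protocol's efficacy endpoints. Add an Extension baseline: the last non-missing value before the Extension Week 0 infusion. Show Extension safety and PD change and shift from it beside the Week 0 change.
- **SAP 5.7.** Add a descriptive Group 2 minus Group 3 difference with 95% CI for ADA positivity, infusion-related reactions and DAS28 (CRP), adjusted for the two Extension strata where counts allow. Name the visits that define ADA positivity: the rule in SAP 13.1.4.3 for the Extension infusion-reaction table also counts positives from Weeks 24 and 48, before any switch. Keep the pooled Group 2 and 4 column if wanted, with a note that it is not a randomised group.

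The cost is SAP wording and a few more table columns. No new data are needed, since Protocol Table 6 already schedules the measurements before dosing at Extension Week 0. The intervals will be wide and unpowered and should be labelled descriptive.

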#### **5.6. Protocol Deviations**

Protocol deviation will be categorized as “major” or “other (or minor)”. Category of protocol deviation will be identified during the Data Review Meeting (DRM). A major protocol deviation is one that may affect the interpretation of study results or the patient’s rights, safety or welfare. Patients with major protocol deviation could be excluded only from the population (PD and/or Efficacy) that would be affected by the deviation.

Major protocol deviations are defined as follows:

- Mis-randomizations (defined as patients who received the another treatment to which they were assigned at any point during the study)
- Non-compliance of inclusion or exclusion criteria (to be identified by the [REDACTED] medical department via review of data sourced from the site monitoring database)
- Significant GCP non-compliance sites (to be identified by [REDACTED] as sites which have been closed due to suspected scientific misconduct and/or serious GCP non-compliance)
- Receipt of prohibited medication (based on agreement of each as from both [REDACTED] and CLT prior to database lock)

The major protocol deviations and other categories used for exclusion will be summarized for the all-randomized population by study part, treatment group. A listing of major protocol deviations for each patient will also be provided by treatment group.

The significant GCP non-compliance site will be excluded in all populations. The information of this site will be only listed in the Demographics and Treatment-emergent Serious Adverse Events listings, separately.

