7.6 Analysis Sets

Five patient populations are defined: PK, efficacy, PD, safety, and all-randomized populations.

The PK population is defined to be all patients who receive at least 2 doses (Week 0 and Week 2) of study drug (CT-P10, Rituxan or MabThera), who provide sufficient blood concentration data to compute the required PK variables, and who do not have any major protocol violation including a violation of the inclusion and exclusion of criteria. The PK population will be the primary population for the summary and analysis of PK data.

The efficacy population is defined to be all patients who receive at least 1 dose of study drug (CT-P10, Rituxan or MabThera), who have at least 1 post-treatment efficacy result, and who do not have any major protocol violation including a violation of the inclusion and exclusion of criteria. The efficacy population will be the primary population for the summary of efficacy data.

The PD population is defined to be all patients receiving at least 1 dose of study drug (CT-P10, Rituxan or MabThera) and providing at least 1 post-treatment PD result. The PD population will be the primary population for the summary of PD data.

The safety population is defined to be all patients who receive at least 1 dose (full or partial) of study drug (CT-P10, Rituxan or MabThera). The safety population will be the primary population for the summary of safety data.

The all-randomized population is defined to be all patients enrolled and randomly assigned to receive a dose of study drug, regardless of whether or not any study drug dosing was completed. All efficacy parameters will also be analyzed for the all-randomized population.

The number of patients, who discontinue from the study prematurely, together with the reasons for discontinuation, will be summarized. In addition, for each analysis population the number of patients will be presented.

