**Table 1: Populations and Subsets of Analysis**

Populations	Subsets
Main Study Period: Part 1	
all-randomized	
safety	
pharmacokinetic	pharmacokinetic (antibody negative subset) pharmacokinetic (antibody positive subset)
Main Study Period: Part 2	
all-randomized	all-randomized (antibody negative subset)
safety	safety – 2 nd treatment course in Main Study Period subset
efficacy	efficacy (antibody negative subset) efficacy (antibody positive subset) efficacy – 2 nd treatment course in Main Study Period subset
pharmacokinetic	pharmacokinetic (antibody negative subset) pharmacokinetic (antibody positive subset) pharmacokinetic – 2 nd treatment course in Main Study Period subset
pharmacodynamic	pharmacodynamic (antibody negative subset) pharmacodynamic – 2 nd treatment course in Main Study Period subset
Extension Study Period	
all-randomized	all-randomized – Extension Study Period subset
safety	safety – Extension Study Period subset
efficacy	efficacy – Extension Study Period subset
pharmacodynamic	pharmacodynamic – Extension Study Period subset

All-randomized, safety and PK populations and its subsets will be defined for the patients from Part 1 and 2, respectively. Efficacy and PD population and its subsets will be defined for the Part 2. Population for Part 2 will include patients from Part 1.

Patients who have any major protocol deviations (as defined in [Section 5.6](#)) may be excluded only from the population (PD and/or Efficacy) that would be affected by the deviation. Patients from the significant GCP non-compliance sites as defined in [Section 5.6](#) will be excluded in all populations.

The number of patients in all populations will be tabulated by the treatment group in each relevant Part and study period. A listing will also be produced, displaying this data.

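### SAP 5.4 and 5.6 remove patients at sites closed for GCP reasons from the safety and all-randomized populations, against the protocol's and the SAP's own definitions, and no safety table includes them

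*SAP*

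**What the plan says.** Protocol 7.6 defines safety by exposure: "The safety population is defined to be all patients who receive at least 1 dose (full or partial) of study drug". It defines the all-randomized set by allocation: "The all-randomized population is defined to be all patients enrolled and randomly assigned to receive a dose of study drug", whether or not dosing took place. Neither definition carries an exception for site or protocol deviation. SAP 5.4.5 and 5.4.1 restate both, also without exception.

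SAP 5.6 lists the major deviations. One item on that list is "sites which have been closed due to suspected scientific misconduct and/or serious GCP non-compliance". For major deviations in general, 5.6 sets a limit: "Patients with major protocol deviation could be excluded only from the population (PD and/or Efficacy) that would be affected by the deviation". Later in the same section comes the site rule: "The significant GCP non-compliance site will be excluded in all populations". The text under Table 1 in SAP 5.4 applies the same rule to "Patients from the significant GCP non-compliance sites".

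For what is kept, 5.6 says: "The information of this site will be only listed in the Demographics and Treatment-emergent Serious Adverse Events listings, separately". SAP 10.3 and 11.2 each add a sensitivity analysis if such sites exist, the first for the primary PK endpoints and the second for the DAS28 ANCOVA. SAP 13 runs the safety analyses on the safety population and its subsets and has no corresponding provision.

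**The concern.** A safety population is meant to hold everyone exposed. Under the site rule, a dosed patient at a closed site contributes to no safety numerator or denominator. Because the retained listings are confined to demographics and treatment-emergent serious events, that patient's other safety data appear nowhere: non-serious adverse events, non-serious infections, non-serious infusion-related reactions, laboratory and immunoglobulin results, and anti-drug antibody results. Infections and infusion reactions are events of special interest in SAP 13.1.4, and SAP 4.1 gives safety and immunogenicity as the purpose of the Extension Study Period.

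The trigger is also broad. A site closed on suspicion meets it, so exposed patients can be removed before anything is established about their data.

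Finally, the rule contradicts other parts of the plan. The protocol and SAP definitions say one thing and the site rule another, and two sentences in SAP 5.6 cannot both be applied to the same patients.

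**Working it through.** The plan states no figure on this point, so the check is mainly a comparison of definitions.

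**Step 1: each population against the site rule.**

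| Population | Protocol 7.6 | SAP definition | Effect of the site rule |
|---|---|---|---|
| Safety | any full or partial dose; no exception | 5.4.5: same | conflicts with both |
| All-randomized | everyone randomized; no exception | 5.4.1: same | conflicts with both |
| PD | one dose and one PD result; no violation clause | 5.4.4: one full dose and one PD result | conflicts with the protocol |
| PK and efficacy | major violators removed | 5.4.2 and 5.4.3 | consistent with the protocol |

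**Step 2: consistency within SAP 5.6.** Closed sites are on the major-deviation list. The general limit allows exclusion from PD and/or efficacy only, while the site rule excludes from every set. Section 5.6 also tabulates major deviations on the all-randomized population. Once these patients have left that population, the closed-site row of the table is empty. The disposition table in SAP 6 uses the same population, so its randomized count would fall short of the number actually randomized.

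**Step 3: what the sensitivity analyses reach.** Primary PK endpoints: covered (10.3). DAS28: covered (11.2, where the ANCOVA is run on both the all-randomized and efficacy populations). Safety and immunogenicity: not covered.

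**Step 4: direction of the effect.** Let an arm have N patients and E patients with an event, and let the closed site hold k of those patients, e of them with the event. The count goes from E to E − e, so it can only fall or stay the same. The rate goes from E/N to (E − e)/(N − k). It falls if e/k is above E/N and rises if e/k is below E/N. The arm difference can therefore move in either direction.

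**Step 5: size.** Inputs: about 361 patients (Protocol 7.5) and about 110 centers (Protocol 4.1).

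- Average site: 361/110 = 3.3 patients; 3.3/361 = 0.9% of the planned total.
- The documents give no site sizes. For an assumed 3, 10, 20 or 40 excluded patients, the share lost is k/361 = 0.8%, 2.8%, 5.5% or 11.1%.
- For an event with an assumed incidence of 5%, the chance that at least one case lies among the excluded patients is 1 − 0.95^k = 14%, 40%, 64% or 87%.

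These shares take all 361 planned patients as dosed.

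**The case against.** The strongest reply is that data from a site closed for misconduct may be wrong. If such a site under-recorded or invented data, keeping it would dilute event rates and could make the arms look more alike, which is a real hazard in a similarity study. This stands as a reason to show results without the site. It does not justify having no table that includes patients who were exposed, and the SAP itself accepts their serious events for listing.

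Several stronger readings are tempting, and the documents do not support them.

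- *That exclusion can only hide events.* This is true of counts. The SAP reports numbers and percentages by arm, and Step 4 shows that percentages and arm differences can move either way.
- *That these patients disappear altogether.* They leave the summaries, but treatment-emergent serious events stay in a separate listing, so deaths, life-threatening events and hospitalizations after dosing remain visible.
- *That the SAP simply breaches the protocol.* Protocol 7.8 allows planned analyses to change if the SAP documents the change. The SAP states the rule openly, in two places. What is missing is any identification or justification of it as a departure from Protocol 7.6.
- *That the primary efficacy result on all randomized patients is left unprotected.* SAP 11.2 attaches a sensitivity analysis to the DAS28 ANCOVA for this situation, although it does not spell out the content.
- *That a site was in fact closed.* The singular wording in 5.6 might suggest one. SAP 5.4 uses the plural, and 10.3 and 11.2 are conditional. Nothing supplied says that any site met the definition.

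**Conclusion.** The inconsistency is established from the text alone. The site rule conflicts with the protocol's safety and all-randomized definitions, with the SAP's own versions of them, and with the limit on exclusions in SAP 5.6. It is not identified as a change from the protocol. Followed as written, it leaves dosed patients at an affected site out of every safety summary, with no safety sensitivity analysis to restore them.

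The practical size is unknown and depends on a site being closed on these grounds; if none is, the rule changes no result. One average site is about 0.9% of patients. The larger shares and the 5% incidence shown above are assumptions. Counts would be understated, but the direction of any effect on rates or arm differences cannot be predicted. This should be corrected because the remedy is cheap and specific, not because a bias has been shown.

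**What to change.** 1. Keep all dosed patients in the safety population and all randomized patients in the all-randomized population, as Protocol 7.6 defines them.
2. Produce the key safety tables (adverse events, events of special interest, laboratory grades, immunogenicity) with and without the affected sites.
3. Limit the site exclusion to the PK and efficacy populations, where the protocol already removes major violators. Protocol 7.6 has no such clause for PD, so any PD exclusion must be documented as a change.
4. Reconcile SAP 5.4 and 5.6: the general limit names PD and/or efficacy, the site rule says all populations, and the protocol's violation clause sits in PK and efficacy. One rule should replace the three.

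If the sponsor prefers to keep the exclusion, the SAP should record and justify it as a departure from Protocol 7.6 and still add safety tables that include these sites.

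The cost is SAP wording and a few repeated tables. The small downside is that the safety tables may carry less reliable records, which the tables without the affected sites address.
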